The study aims to recruit 40-70 normolipidemic healthy individuals aged 18-65 years. The study will last for 35 days. The E-EPA-supplementation will last for 28 days, followed by a seven-day washout period. Blood samples are taken before (day 0), during day (day 7), after (day 28) the E-EPA-supplementation and after the washout period (day 35). At day 0 visit, participants will undergo a health examination (inclusive an interview, health questionnaire, anthropometric measurements, blood pressure measurement) and blood withdrawal. The blood will undergo laboratory analyses including complete blood count and key metabolic biomarkers (total cholesterol, LDL cholesterol, HDL cholesterol, triglycerides, apoB-100, apoA-I, and Lp(a), vitamin D3, and blood glucose).

Individuals with exceptionally low LDL aggregation susceptibility will be excluded, as further investigation of their LDL particles would not be meaningful in the present context. Additional exclusion criteria include pregnancy, known blood coagulation disorders, LDL cholesterol >5 mmol/L, triglycerides >3 mmol/L, regular use of anti-inflammatory drugs, and fish allergy.

Supplementation

We will follow the dosing model used in the REDUCE-IT (Bhatt *et al.*, 2019) study, administering 2 grams of pure E-EPA twice daily with meals. Pure E-EPA is not commercially available in Finland, and thus a supplement containing 650 mg of E-EPA and 12.5 μ g of vitamin D3 per capsule will be employed. The supplement will be provided as three capsules to be consumed in the morning and three in the evening, providing a daily total of 3.9 g of E-EPA and 75 μ g of vitamin D3.

Based on previous studies, vitamin D3 is not expected to influence the primary outcome variables. The internationally accepted maximum tolerable daily intake of vitamin D3 for long-term use is 100 μ g. In Finland, the estimated daily dietary intake of vitamin D3 ranges between 10-20 μ g, suggesting that overall vitamin D3-dosage will remain well within safe limits even with the increased intake provided by the supplement. Notably, the participants will be instructed not to use other (commercial) vitamin D supplements during the study.

Research Methods

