This study is a **single-arm, longitudinal nutritional intervention study with a repeated-measures design**, investigating the effects of icosapent ethyl on blood composition and functional parameters in healthy, normolipidemic volunteers. A total of 38 participants were recruited and screened for inclusion and exclusion criteria based on an initial blood draw. Eligible participants provided a baseline blood sample at Day 0 before receiving the intervention. Participants consumed the supplement daily for four weeks (Days 1–28), with blood samples collected at Days 7 and 28. Following the intervention period, participants underwent a 7-day washout phase, after which a final blood sample was collected at Day 35. No control or placebo group was included in the study, as each participant served as their own control through repeated within-subject comparisons over time.

1. Statistical Methods

The statistical methods employed in this study include tests for normality, group differences, analysis of variance, correlation analysis, time series clustering, principal component analysis (PCA), linear mixed modeling, hierarchical clustering, distance calculations, sparse partial least squares-discriminant analysis (sPLS-DA), uniform manifold approximation projection (UMAP), and machine learning models. Specific methods include:

- **Normality Testing:** D'Agostino-Pearson omnibus K2 test.
- **Group Differences:** Paired multiple t-tests (LIMMA) on log2-transformed data, with false discovery rate (FDR) correction.
- **Analysis of Variance:** One-way ANOVA with post hoc analysis (Benjamini, Krieger, and Yekutieli FDR correction).
- **Correlation Analysis:** Spearman's correlation with exact p-values for small datasets and t-ratio derived p-values for larger datasets.
- **Time Series Clustering:** VSClust fuzzy c-means clustering with k-nearest neighbors (kNN) imputation for missing values.
- **PCA:** Performed on log2-normalized lipid abundances, using centering and scaling.
- **Linear Mixed Modeling:** Implemented using lmer in the lme4 package, with time as a fixed effect and subject as a random effect.
- **Hierarchical Clustering:** Ward's method applied to Euclidean distance matrices from PCA scores.
- **Distance Calculations:** Euclidean distances calculated from PCA scores to assess intra- and inter-subject variability.
- **sPLS-DA:** Conducted via MetaboAnalyst 6.0 with nested cross-validation.

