- **UMAP:** Dimensionality reduction using the umap package with predefined parameters.
- **Machine Learning:** XGBoost regression models trained on lipidomic and clinical data using nested cross-validation.

No formal interim analysis was planned.

2. Sample Size and Power Justification

The study initially planned to enrol 40–70 participants, with a total of 72 recruited and 68 enrolled. Due to COVID-19 restrictions, only 38 participants completed the study. A formal power calculation was not conducted, and sample size selection was based on feasibility and the exploratory nature of the study. The final analysis will include only the 38 participants who completed the study.

A sample size assessment was conducted post hoc to evaluate whether the study had sufficient statistical power to detect changes in LDL aggregation, triglycerides, and EPA incorporation. This assessment was based on observed variability in the data and repeated-measures ANOVA. The observed effect size was computed using partial eta-squared ($\eta^2 p$). The effect size was then converted to Cohen's f and used to estimate the required sample size for 80% power. The results indicated that for the primary outcomes, the study had sufficient power to detect moderate-to-large effects, with a required sample size of approximately 16 participants for the observed effect sizes.

3. Level of Significance

A two-tailed significance level of 0.05 was used throughout the study. Multiple hypothesis testing corrections were applied using the false discovery rate (FDR) method where appropriate.

4. Criteria for Termination of the Trial

The trial would be terminated if more than 10% of the participants encountered adverse effects related to the intervention.

5. Handling of Missing Data

A complete case analysis approach was used for analyses requiring full datasets, such as UMAP, PCA, and machine learning analyses. Within these complete cases, missing values were handled using k-nearest neighbors (kNN) imputation where required. However, for single-variable analyses, all available data were used, and missing values were omitted rather than imputed.

6. Deviations from the Original Statistical Plan

The study deviated from the original protocol in the following ways:

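### The mixed model's only random term is subject, so where it supplies a reported visit contrast, the Day 28 vs Day 0 standard error can be too small, by an amount the documents do not fix

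*Combined protocol and SAP*

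**What the plan says.** Section 1 of the SAP lists its methods. The mixed model entry reads "Implemented using lmer in the lme4 package", "with time as a fixed effect and subject as a random effect". It names no random slope, visit-specific variance, correlation structure, robust standard error or degrees-of-freedom method, and it does not say whether time is a factor or a number of days.

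The SAP introduction gives the schedule: "Eligible participants provided a baseline blood sample at Day 0 before receiving the intervention", then a four-week supplementation period "with blood samples collected at Days 7 and 28", then a washout "after which a final blood sample was collected at Day 35". The protocol (Section III, Study Population) has the same four days. There is no control arm; the SAP says that "each participant served as their own control through repeated within-subject comparisons over time".

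On the data set, SAP Sections 2 and 7 say: "The final analysis will include only the 38 participants who completed the study". Section 7 also drops anyone with a missing time point, which makes the data balanced. Section 5 lets single-variable analyses use whatever data are available, which could leave them slightly unbalanced.

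The same list in Section 1 includes LIMMA paired t-tests and a one-way ANOVA. Nothing says which method produces which reported contrast.

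**The concern.** A single subject effect imposes compound symmetry: one residual variance, and one correlation shared by every pair of visits. The design gives reason to doubt this. The gaps between visits are 7, 21 and 7 days, so correlation may fade over the longer intervals. Day 28 minus Day 0 also compares the end of supplementation with baseline. If people respond to different degrees, that difference carries the full spread of individual responses, while most other differences carry part of it.

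Without a control arm, every conclusion is a within-subject visit difference, tested at the two-sided 0.05 level of SAP Section 3. If such a difference comes from this model and its standard error is too small, the change is reported as more certain than the data support. FDR adjustment does not repair this, because it takes the p-values as given. A sphericity correction to an ANOVA does not help either: it alters the omnibus F test and leaves the lmer contrasts as they were.

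**Working it through.** The plan gives no standard error or covariance to reproduce. Its nearest figure, about 16 participants for 80% power (SAP Section 2), comes from a repeated-measures ANOVA whose effect size is not printed. It cannot be rebuilt, and nothing below depends on it.

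**Inputs from the documents.** n = 38; visits at Days 0, 7, 28 and 35; two-sided alpha 0.05. **Assumed:** visit is a factor, data are complete, the subject effect is a random intercept with positive estimated variance, tests use the pooled error degrees of freedom, and the covariance is as stated in each scenario.

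**Step 1: one standard error for all contrasts.** Under these conditions each visit difference has SE = √(2·MSE/n). Since 2·MSE equals the mean of the six sample variances of the paired differences, the model's squared SE is the mean of the six squared paired SEs.

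Check on one simulated data set of 38 people with varying response. The paired SEs were 0.2435 (7 vs 0), 0.3110 (28 vs 0), 0.2470 (35 vs 0), 0.1931 (28 vs 7), 0.2261 (35 vs 7) and 0.2547 (35 vs 28). Their squares sum to 0.3703, and √(0.3703/6) = 0.2484. The fitted random-intercept model returned 0.2484 for all six.

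**Step 2: ratio of model SE to true SE for Day 28 vs Day 0.** In expectation this is √(mean of six true difference variances ÷ true variance of Day 28 minus Day 0).

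*Correlation decaying at r per week.* Each difference variance is proportional to 1 − r^w, with w = 1, 4, 5, 3, 4, 1 weeks for the six pairs.
- r = 0.80: mean 0.4569; Day 28 vs 0: 1 − 0.4096 = 0.5904; ratio √(0.4569/0.5904) = 0.88. Day 7 vs 0: √(0.4569/0.20) = 1.51.
- r = 0.95: mean 0.1400; Day 28 vs 0: 0.1855; ratio 0.87. Day 7 vs 0: √(0.1400/0.05) = 1.67.

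*The same with independent visit-level noise,* as a fraction c of the decaying variance. Add c to numerator and denominator.
- c = 0.25: √(0.7069/0.8404) = 0.92 (r = 0.80) and √(0.3900/0.4355) = 0.95 (r = 0.95).
- c = 1: 0.96 and 0.98.

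*Response varying between people,* with response variance v times the residual variance, and shares 0, 0.5, 1 and 0.25 of the response at the four visits. Each difference variance is 2 + v·(difference in shares)². The six squared share differences are 0.25, 1, 0.0625, 0.25, 0.0625 and 0.5625, with mean 0.3646.
- v = 0.25: √(2.0911/2.25) = 0.96. v = 0.5: √(2.1823/2.5) = 0.93.
- v = 1: √(2.3646/3) = 0.89. v = 2: √(2.7292/4) = 0.83.

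**Step 3: type I error by simulation** (n = 38, no true mean change, 20,000 runs per scenario; model contrasts on (38 − 1)(4 − 1) = 111 df):

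| Assumed covariance | Day 28 vs 0 SE too small by | Type I error |
|---|---|---|
| Compound symmetry | 0% | about 5% |
| Decay plus noise, c = 1 | 2-4% | 5.4-5.9% |
| Varying response, v = 0.25-0.5 | 4-7% | 5.8-6.3% |
| Decay plus noise, c = 0.25 | 5-8% | 6.5-7.1% |
| Pure decay, r = 0.80-0.95 | 12-13% | 8.6-9.6% |
| Varying response, v = 1-2 | 11-17% | 7.7-10.6% |

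Paired differences (37 df) held about 5% throughout. A more extreme assumption, with response SD twice the residual SD (v = 4) and several patterns of build-up and washout, gave an SE 18-25% too small and type I error of 11-14%.

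**Step 4: other contrasts.** Under pure decay the Day 7 vs 0 SE is 51-67% too large. With noise added this falls to 14-25% (c = 0.25) and 4-10% (c = 1). In the varying-response scenario of Step 2 with v = 1-2 it is only 2-5% too large (√(2.3646/2.25) = 1.02; √(2.7292/2.5) = 1.04). If the whole response is already present at Day 7 and still present at Day 35 (v = 1), that SE is instead about 9% too small (ratio 0.91). No single direction holds.

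**The case against.** The strongest objection is about reach. lmer is one of a dozen listed methods, and nothing ties it to the Day 28 vs Day 0 result. The entry for group differences is LIMMA paired testing, which, fitted pair by pair, has a contrast-specific error and avoids the problem. The post hoc power check uses a repeated-measures ANOVA. This stands: the point affects a reported result only where lmer is its source.

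The premises are also unstated. If time were entered as linear days, standard errors would scale with the gap instead of being equal, though a straight line could not follow the washout. If Section 5 rather than Section 7 governs missing visits, the standard errors would be nearly rather than exactly equal. These limits stand too.

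A reader might infer that the trial's error bars are wrong in both directions, or that its Day 28 finding has a false-positive rate of 8-11%. The documents support neither. They give no SD or correlation for any visit; the error vanishes under compound symmetry and could reverse if Day 28 minus Day 0 varies less than the average difference. The aggregation assay passes through ultracentrifugation, enzymatic modification and light scattering, so appreciable measurement noise is plausible, and noise shrinks the error.

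Finally, the study describes itself as exploratory, and a random intercept is a common default. That lowers the stakes. It does not make a common standard error appropriate where a contrast-specific one is readily available.

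**Conclusion.** The concern holds conditionally. With subject as the only random term, visit as a factor and balanced data, the equal standard errors follow by algebra. Whether the one for Day 28 vs Day 0 is too small depends on whether that difference varies more than the six-pair average. The schedule and the on-off design make this plausible; the documents do not establish it.

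The size is an assumption: nil under compound symmetry, about 2-8% in the milder cases (type I error about 5-7%), and about 11-17% with strong response variation or pure time decay (about 8-11%). It rests on the assumed covariances, the 111 df test and lmer being the source of the contrast. It is a change worth making because it is cheap, and because the SAP leaves a reader unable to tell whether the main contrast is affected.

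**What to change.** In SAP Section 1:
- State that visit is a four-level factor, and name the method that supplies each reported contrast.
- Take each contrast now assigned to lmer from per-pair paired differences, or from a model with unstructured within-subject covariance. That covariance has 4 variances and 6 covariances, 10 parameters from 38 × 4 = 152 observations. Plain lmer does not fit this residual structure; gls or mmrm are examples that do.
- If LIMMA supplies the contrast, say that it is fitted pair by pair.
- Keep the random-intercept lmer as a sensitivity analysis, and report the SDs of the six paired differences so that readers can judge the equal-variance assumption.

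The cost is a few sentences and a refit of existing data in a different package. Each contrast has about 37 rather than 111 degrees of freedom, so the critical t rises from 1.98 to 2.03. No new data are needed.

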Breakfast for the participants	500 €
Combined	32 100€

IV. ETHICAL CONSIDERATIONS

The study adheres to Good Clinical Practice (GCP) guidelines, the study plan, and applicable regulations. The study plan aligns with the research objectives and provides sufficient guidance for the research staff to conduct the study appropriately. The research methods used are well-established.

Participants will provide four fasting blood samples over a five-week period. These samples will be analysed for LDL cholesterol, HDL cholesterol, apoB-100, apoA-I, Lp(a), and triglyceride levels. Blood pressure measurements will also be taken during study visits. Participants will receive a summary of these measurements after analyses have been concluded. Prior to each blood sample collection, participants will complete a 24-hour dietary record. As the results related to lipoprotein aggregation and lipidomics remain at an experimental and theoretical level, their clinical significance cannot be assessed at an individual level, and therefore, individual reports on these results will not be provided to participants. However, participants may access study findings after the study has concluded and the results have been published.

E-EPA has not been associated with harmful side effects. Since fish oil-based E-EPA does not contain fish protein, it is generally safe for use; however, due to the high dosage, individuals with fish allergies will not be included in the study. EPA has blood-thinning effects, making anticoagulant medication a contraindication for participation. In the REDUCE-IT trial, 2.3% of E-EPA users reported joint pain, compared to 1% in the placebo group. The amount of vitamin D3 administered in the study exceeds Finland's daily recommended intake but remains well below the EU's upper safe limit of 100 µg, which has been shown to have no adverse effects. Participants taking daily vitamin D3 supplements will be requested to discontinue their use minimum one week prior to commencing the study. Vitamin D3 levels in the blood will be monitored for potential side effects.

Participants may withdraw from the study or revoke their consent at any point prior to its conclusion without any repercussions. Any data collected before consent withdrawal will be used if deemed necessary for the accuracy and reliability of overall study results.

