- **Sample Size Reduction:** The original plan aimed for 40–70 participants, but only 38 completed the study due to COVID-19 restrictions. The final analysis includes only these 38 participants under a per-protocol approach rather than an intention-to-treat model.
- **Changes in Outcome Assessments:** Some planned secondary outcomes, including enzyme activity assays (PLTP, CETP, PON-1, LCAT) and ELISA assays for ANGPTLs and resolvins, were not conducted due to COVID-19-related constraints.
- **Changes in study collaborators:** Due to Covid-19 travel restrictions and delays, the international collaboration with Karolinska Institute was halted and [name] [name] and PhD [name] removed from the research team.

- **Expanded Statistical Methods:** The study incorporated additional statistical methods, including machine learning (XGBoost), time series clustering (VSClust), hierarchical clustering, UMAP, and sPLS-DA, which were not in the original protocol.
- **Data Handling Approach:** The original plan allowed for analysis of partially completed cases, but the final study adopted a complete case analysis approach, excluding participants with missing time points.
- **Stopping Criteria Introduced:** The original plan did not specify stopping rules. The final study introduced a stopping rule stating that if >10% of participants experienced adverse effects, the study would be terminated.

These modifications were made to accommodate study constraints while maintaining scientific rigor.

7. Selection of Subjects for Analysis

The final analysis will include only the 38 participants who completed the study, following a per-protocol approach. Participants with missing time points will not be included in the analysis.

8. Direct Access to Source Data/Documents

The study sponsor will ensure that the investigator(s)/institution(s) permit trial-related monitoring, audits, IRB/IEC review, and regulatory inspection(s), providing direct access to source data/documents. The source data will not be made publicly available in any repository due to legislation on anonymity. Data is stored on secure backup media and deposited on a secure university server for long-term storage and controlled access.

9. Quality Control and Quality Assurance

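### The sPLS-DA entry names neither its classes nor any handling of repeated samples from one person; sample-level classification of visits would understate separation and can distort cross-validation.

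*Combined protocol and SAP*

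**What the plan says.** The introduction to the statistical analysis plan describes a single-arm repeated-measures study in which "each participant served as their own control through repeated within-subject comparisons over time". The protocol (Ethical Considerations) gives the sampling: "Participants will provide four fasting blood samples over a five-week period", at days 0, 7, 28 and 35. SAP Section 7 restricts the analysis set to 38 completers and adds "Participants with missing time points will not be included in the analysis", so every analysed person is present at every visit.

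SAP Section 1 states the within-person structure for two methods. Group differences use "Paired multiple t-tests (LIMMA) on log2-transformed data, with false discovery rate (FDR) correction", and the mixed model is fitted "with time as a fixed effect and subject as a random effect". The whole sPLS-DA entry is "Conducted via MetaboAnalyst 6.0 with nested cross-validation". It does not state the classes, the pre-processing or scaling, a paired or multilevel option, or how samples are assigned to folds. Centring and scaling are stated for PCA only. Section 6 lists sPLS-DA among the methods added later: "hierarchical clustering, UMAP, and sPLS-DA, which were not in the original protocol".

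**The concern.** With no comparison group, visits are the natural classes for sPLS-DA, and every participant then belongs to every class. Standard sPLS-DA has no participant term. Applied to individual samples, it treats stable differences between people as noise around each visit, although the design was chosen so that these differences could be removed.

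Three outputs are at stake: the displayed separation between visits, the cross-validated error, and whatever is tuned on that error (number of components, number of lipids kept). Cross-validation carries a further risk. If one of a person's samples is in the training set and another in the test set, the test sample resembles a training sample that, by design, carries a different visit label. That pulls its prediction towards the wrong class.

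**Working it through.** **Inputs from the documents.** 38 participants; four visits, so 38 × 4 = 152 samples if complete; all participants at all visits. The documents report no sPLS-DA error rate, so there is no plan figure to reproduce. The only power figure, about 16 participants in SAP Section 2, comes from repeated-measures ANOVA on other outcomes.

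**Assumed inputs.** The documents give no between- or within-person variance. Main scenario: Day 0 versus Day 28, 150 lipids, 10 truly shifted by δ = 0.4, within-person SD σw = 0.5, between-person SD σb from 0.4 to 1.6 across lipids. The intraclass correlation σb²/(σb² + σw²) then runs from 0.16/0.41 = 0.39 to 2.56/2.81 = 0.91.

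**Step 1: one lipid.** A single sample is classified correctly with probability Φ(δ / (2√(σb² + σw²))). With σb = 1.0 this is Φ(0.4 / (2 × 1.118)) = Φ(0.179) = 57%. After centring over two visits it is Φ(δ / (√2 σw)) = Φ(0.4/0.707) = Φ(0.566) = 71%. The second formula is also the chance that the person's two raw samples fall in the right order. For one lipid, then, the whole gain comes from comparing two samples of the same person.

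**Step 2: full classifier, main scenario.** Two components, 20 selected lipids, 5-fold cross-validation:

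| Data | Folds | Scoring | Accuracy |
|---|---|---|---|
| Raw | by sample | single sample | 43% |
| Raw | by participant | single sample | 66% |
| Raw | by participant | within-person order | 84% |
| Centred | by participant | single sample | 89% |

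With δ = 0.3, raw data give 33% with folds by sample and 60% with folds by participant; centred data give 76.5%.

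**Step 3: dependence on the intraclass correlation (ICC).** A second simulation used 38 people, 200 lipids, 20 of them shifted by one within-person SD, two visits and the same ICC for every lipid. Cross-validated error:

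| ICC | Raw, folds by sample | Raw, folds by participant | Centred |
|---|---|---|---|
| 0 | 3.5% | 3.5% | 0.4% |
| 0.5 | 11% | 10% | 0.6% |
| 0.7 | 18% | 15% | 0.5% |
| 0.9 | 44% | 26% | 0.8% |

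Centring helps even at ICC 0, which again shows that it uses two samples where the raw model uses one. With a shift of 0.5 SD and ICC 0.9, the errors are 72%, 42% and 22.5%; the first is well above the 50% expected by chance. With four visits, the same shift and the same ICC they are 90%, 71% and 65.5%, where chance is 75%.

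**Step 4: lipid selection.** The first component depends on X′Y. Person i contributes (person mean) × Σv(y_iv − 1/V) for each class, where y_iv is 1 if visit v is that class and V is the number of visits. With complete visits the sum is 1 − 1 = 0, so person means drop out. Numerically, raw and centred X′Y differ by about 1e-14.

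Unit-variance scaling breaks this, because each raw lipid is divided by its total SD. For a shifted lipid the first-component signal is δ/√(σw² + σb² + δ²/4):
- σb = 0.4: 0.4/√0.45 = 0.60.
- σb = 1.6: 0.4/√2.85 = 0.24, about 2.5 times smaller for the same true change.
- Centred: 0.4/√(0.125 + 0.04) = 0.98, whatever σb is.

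Simulated recovery of the truly changed lipids in the main scenario is 70% raw versus 82% centred with scaling, and 82% versus 82% without. With scaling, among the five changed lipids with the highest between-person SD, recovery is 51% versus 80%. With equal between-person SD it is 81% versus 81%. In the equal-ICC simulation (two visits, 1 SD shift) the selected panels are 90–94% correct raw and 92–94% centred.

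**The case against.** The strongest reply is that the SAP is silent rather than wrong. It nowhere says that samples are treated as independent, and Section 14 refers to Supplementary Methods that are not part of these documents. A reader might infer that the analysis definitely ignored pairing; the text does not establish that. This stands, and the point is therefore conditional.

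Second, the classes need not be visits. The SAP also plans hierarchical clustering and an assessment of inter-subject variability, so participant-level groups are possible. Centring by participant would then erase the contrast of interest. This stands as a limit on the fix.

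Third, the comparison of 66% with 89% is not like for like. Most of it closes when the raw model is scored by within-person order (84% versus 89%). This stands too: a reader might conclude that person-to-person differences bury the supplement effect, but the figures do not show that. It does not rescue sample-level error as a summary of an own-control study, nor folds that split a person.

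Fourth, it is tempting to say that the lipid panel drifts towards species with low between-person variance. Step 4 shows this needs both unit-variance scaling and unequal between-person variances. The SAP states neither for sPLS-DA.

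Finally, sPLS-DA is one added method in an exploratory study. Paired LIMMA and the mixed model still estimate the within-person change, so a reader should not infer that the answer on LDL composition depends on this entry. The understatement of separation is also conservative. Both points limit the severity without removing the gap.

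**Conclusion.** The concern holds in conditional form. The sPLS-DA entry is under-specified in three respects that matter in this design: classes, within-participant handling and fold assignment. If visits are classified with standard sample-level sPLS-DA, separation is understated. If folds also split a person's samples, cross-validated error and tuning are distorted, and accuracy can fall below chance (43% in the main scenario). Any tilt in lipid selection is conditional on scaling together with unequal between-person variances; otherwise first-component selection is essentially unchanged.

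All sizes rest on assumed variances and shifts, and the effect grows with an intraclass correlation that the documents do not give. This is a worthwhile correction to a supporting analysis. It does not challenge the estimates of within-person change.

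**What to change.** In SAP Section 1, name the sPLS-DA classes and state the scaling. For visit comparisons:

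- subtract each participant's mean across the compared visits from the log2 abundances (multilevel decomposition) before sPLS-DA;
- assign folds by participant in both the inner and the outer loop;
- report that panel as the main sPLS-DA result, labelled exploratory and secondary to paired LIMMA and the mixed model;
- state that the centred accuracy describes the ordering of samples within a person, not the classification of a single sample.

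Do not centre by participant if the classes are participant-level groups. In that case, say so and still keep each person's samples in one fold.

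The cost is one pre-processing step and a re-run on existing data. Because participants with missing time points are excluded, the data are balanced and centring is simple. If this was already done, one added sentence in the SAP closes the point.

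### The only stopping rule is worded two ways on relatedness, its base is undefined and no safety set is named, so for some adverse-effect counts the plan does not settle whether the threshold was crossed

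*Combined protocol and SAP*

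**What the plan says.** The rule appears twice in the SAP.

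- Section 4, which sets the termination criteria, reads: "The trial would be terminated if more than 10% of the participants encountered adverse effects related to the intervention".
- Section 6 (Deviations from the Original Statistical Plan): "The original plan did not specify stopping rules", followed by "The final study introduced a stopping rule stating that if >10% of participants experienced adverse effects, the study would be terminated".

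The possible bases come from three places.

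- Section 2 describes enrolment as "with a total of 72 recruited and 68 enrolled", and says that because of COVID-19 restrictions "only 38 participants completed the study".
- The opening paragraph of the SAP gives a different account: "A total of 38 participants were recruited and screened for inclusion and exclusion criteria based on an initial blood draw".
- Section 7 (Selection of Subjects for Analysis) fixes the analysis set: "The final analysis will include only the 38 participants who completed the study, following a per-protocol approach".

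No separate set for adverse effects is defined. The only safety monitoring described is the blood vitamin D3 measurement in the protocol's Ethical Considerations. Neither document describes how adverse effects were collected or how relatedness was judged.

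**The concern.** This is the trial's only stated safety decision rule. A rule of this kind needs a numerator (which events count) and a base (which people count). Here the numerator is worded in two ways and the base is left to the reader. In a single-arm study with no placebo group, relatedness is a judgement, so the qualifier can change the count materially.

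The analysis set adds a separate reporting question. Section 7 places 30 of 68 enrolled people outside the final analysis and names no other set. If the adverse-effect table follows Section 7, events among those 30 will not appear in it. That the trial has finished does not dispose of the point, because a reader of the report will want to know whether the threshold was crossed, and on what definition.

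**Working it through.** **Inputs.** The threshold is more than 10% (Sections 4 and 6). Section 2 gives 68 enrolled and 38 completed, so 68 − 38 = 30 enrolled people did not complete (30/68 = 44%). The SAP gives no derivation of the 10%, so there is no figure to reproduce.

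**Step 1: the base.** The smallest count above 10% of N is floor(0.10 × N) + 1.

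- N = 38: 0.10 × 38 = 3.8, so 4 affected (4/38 = 10.5%).
- N = 68: 0.10 × 68 = 6.8, so 7 affected (7/68 = 10.3%).
- If the base is those dosed, and all 38 completers were dosed, N lies between 38 and 68 and the crossing count between 4 and 7. The number dosed is not stated.

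With the count held fixed across bases (all affected people being completers):

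| Affected | of 38 | of 68 | Crosses 10%? |
|---|---|---|---|
| 3 | 7.9% | 4.4% | neither |
| 4 | 10.5% | 5.9% | 38 only |
| 5 | 13.2% | 7.4% | 38 only |
| 6 | 15.8% | 8.8% | 38 only |
| 7 | 18.4% | 10.3% | both |

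**Step 2: affected non-completers.** Let t be the number affected among the 68 and c the number of those who completed. The completers base crosses when c ≥ 4, the enrolled base when t ≥ 7. The disagreement can therefore run the other way. Suppose t = 7 and 4 of the 7 did not complete: 7/68 = 10.3% crosses, while c = 3 gives 3/38 = 7.9%, which does not. This is a hypothetical example.

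**Step 3: relatedness.** Any-cause counts are at least as large as related counts. On a base of 38, 3 related and 4 any-cause (7.9% and 10.5%) give opposite answers. On 68, 6 related and 7 any-cause (8.8% and 10.3%) do the same. If both counts lie on the same side of the threshold, the wording makes no difference.

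**Step 4: how often the base would matter.** The exact binomial chance of reaching the crossing count r is P(X ≥ r) = Σ C(N,k) p^k (1−p)^(N−k), summed over k = r to N.

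| True rate p | N = 38, r = 4 | N = 68, r = 7 |
|---|---|---|
| 2.3% | 1.1% | 0.1% |
| 5% (assumed) | 12.0% | 5.3% |
| 10% (assumed) | 53.5% | 52.7% |

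The 2.3% is the joint-pain figure that the protocol cites from an outside trial, the only adverse-effect rate for E-EPA users in the documents. It covers one symptom, so it indicates scale and does not forecast the overall rate.

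**The case against.** The strongest reply is that Section 4 is the operative section and Section 6 only records that a rule was added. On that view the missing qualifier is shorthand, and participants has its ordinary meaning. This is a plausible reading. However, the Section 6 sentence describes the rule of the final study and not superseded text, and nothing in it refers back to Section 4. The two should therefore match.

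Several stronger readings are tempting and are not supported.

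- **That Section 6 counts all adverse effects.** It omits the qualifier; it does not say all or any.
- **That the rule has no denominator.** Both versions name participants; the term is undefined, not absent. A base of 72 recruited adds little, since nothing suggests that the 4 people recruited but not enrolled (72 − 68) took the supplement.
- **That the stopping rule was applied to completers and is biased downward.** Section 7 governs the final analysis, and no text ties the stopping rule to that set. A rule for ending a running trial could hardly be applied to eventual completers. The SAP attributes the shortfall to COVID-19 restrictions, not adverse effects. A downward bias would need affected people to leave more often, which the documents do not state.
- **That it cannot be determined whether this trial crossed its threshold.** This holds only for some counts. A plan is not expected to report counts, and their absence is no defect.
- **That the rule would trigger too easily.** A single event among the first 9 people exceeds 10% (1/9 = 11.1%), but no text describes a participant-by-participant check, and the SAP foresees no formal interim analysis.

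It is also fair to say that, at low event rates, crossing is unlikely on either base.

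**Conclusion.** The point holds as a defect of definition with a bounded effect. The rule is inconsistent on relatedness and its base is undefined. With the count held fixed, 3 or fewer affected cross on neither base, 7 or more cross on both 38 and 68, and 4 to 6 cross on 38 only. Relatedness matters only when the related and any-cause counts straddle the threshold.

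The reporting gap is conditional. It arises if adverse effects are tabulated on the Section 7 set, in which case up to 30 enrolled people are left out; how many of them took any supplement is not stated. The documents do not show that the threshold was crossed, that anyone left because of an adverse effect, or that events were hidden.

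The crossing counts rest on the SAP's own figures. The 5% and 10% rates and the example of 4 affected non-completers are assumptions, and the conclusion does not depend on them. The sponsor should make the change, although it does not affect the efficacy analysis.

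**What to change.** 1. Reconcile SAP Sections 4 and 6 so that both state the same numerator and the same base, as actually applied during the trial. Which clinical rule applies is for the sponsor to state; this review does not choose one.
2. Reconcile the opening paragraph of the SAP with Section 2 on how many people were recruited, so that the base can be traced.
3. Exempt safety from the completers-only restriction in Section 7. Report the number of participants with any adverse effect, and the number with a related one, among all who took any supplement, and give the number dosed. This defines the reporting set and does not settle the base of the stopping rule.
4. State whether the reconciled threshold was crossed.

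The cost is a few lines of SAP wording and one extra table. The table depends on what was recorded: since no collection or causality method is described, it can be completed only as far as the records allow, and any gap should be stated. The downside is that the rate may look less favourable than among completers.
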